Mobilization of Fluid and Fluid Flows in Hemodialysis

21st March 2024

STUDY PROTOCOL**MVVH****Title**

Mobilization of Fluid and Fluid Flows in Hemodialysis

Short title: Fluid Flows in Hemodialysis

Contact Information Principal investigator

[name]

Associate Professor

Department of Anesthesiology and Intensive Care
University Hospital
[name]

Co investigator

[name]

Department of Anesthesiology and Intensive Care
Vrinnevi Hospital Norrköping
[name]

[name]

Director

Department of Anesthesiology and Intensive Care
Vrinnevi Hospital Norrköping
[name]

[name]

Department of Medicine

Vrinnevi Hospital Norrköping
[name]

[name]

Department of Medicine

Vrinnevi Hospital Norrköping
[name]

[name]

Professor

Karolinska Institute Danderyd Hospital (KIDS),
Stockholm

Trial site:

Dialysis Department

Vrinnevi Hospital

Norrköping

Synopsis

During dialysis, three goals are achieved: 1. Blood is cleansed of waste products. 2. Excess water is removed. 3. Electrolytes are regulated. These processes occur simultaneously but vary from patient to patient depending on their specific needs. Some patients have residual urine production but of poor quality. Others have no residual urine production at all and require removal of fluid from both blood and tissues. Episodes of hypotension may occur during dialysis. These are related to intravascular hypovolemia and inadequate fluid reinfusion, which is common with fluid removal exceeding 400 ml/hour. The rate of fluid removal is influenced by fluid recruitment from the tissues. This mainly occurs in two different ways: either through osmotic recruitment across the capillary membranes from the perivascular space or via lymphatic return. The proportions are not yet clear. When fluid recruitment from the perivascular space occurs, influx of albumin and immunoglobulins is unlikely. This differs from lymph, where albumin and immunoglobulins are present. This difference in protein content can be used to calculate the different proportions of fluid recruited from the tissues. This is performed with mass balance calculations based on fluid removal, colloid osmotic pressure, hemoglobin, albumin, and immunoglobulin concentrations.

The rate and proportions of fluid reinfusion into the bloodstream are not yet clarified. Hence the purpose of this study, is to explore these aspects.

Background

In Sweden, approximately 3200 patients are treated annually with hemodialysis¹. In some cases, the goal is solely blood purification, but for most patients, there is also a need to remove excess fluid accumulated since the last dialysis treatment. The amount of fluid removal is prescribed by the dialysis physician and depends primarily on how much secondary urine the patient produces but also on the patient's fluid intake between dialysis treatments.

The most common complication of hemodialysis is hypotension during treatment, occurring in about 10% of treatment sessions according to previous studies. These hypotensive episodes lead to temporary hypoperfusion, and repeated episodes can result in permanent organ damage².

The main cause of these hypotensive episodes is the decrease in circulating volume associated with ultrafiltration, i.e., fluid removal³. The excess fluid accumulated by the patient between treatments mostly resides outside the bloodstream. Therefore, during fluid removal in hemodialysis, there is compensatory recruitment of fluid into circulation, which increases the circulating volume and prevents hypotension. How this recruitment occurs and from which fluid compartments fluid is recruited has not been mapped.

To increase understanding of hemodialysis and optimize treatment while minimizing the risk of hypotension, it is of interest to understand how fluid recruitment occurs and from which fluid compartments the recruitment occurs.

With the help of fluid kinetic calculations, it has in connection with albumin infusion been possible to measure whether fluid is recruited perivascularly or from the lymphatic system depending on the concentration of proteins such as IgG and IgM over time⁴.

Purpose and Objectives

The aim is to study:

- How much fluid is drawn from the interstitial space during dialysis, depending on whether fluid removal is needed or not.
- The size and rate of fluid reinfusion during ongoing dialysis.
- The composition of the recruited fluid from the interstitium, i.e., the proportion consisting of lymph/lymphatic return and the proportion recruited across capillary membranes/venulae from the pericapillary space.

Hypotheses

The null hypothesis is that we do not find any detectable difference in fluid flows or source of fluid recruitment between patients undergoing extensive dialysis and those patients who do not have significant fluid removal during dialysis.

The alternative hypothesis is that we find a clinically relevant difference in fluid flows from the tissues and the pathway of fluid recruitment to the bloodstream.

Outcome Measures

Primary outcome variables are:

Recruitment of fluid from the interstitium calculated from fluid removal and hemoglobin changes.^{5,6}

Proportion of recruited fluid via lymph or via capillary/venular walls based on fluid recruitment and changes in plasma albumin and immunoglobulins G and M.

Secondary outcome variables are:

Weight, blood pressure and changes in bioimpedance variables.

Study Design

Open-label, prospective clinical observational study, where patients are divided into two groups. One group patients with sufficient urine production and dialysis performed solely to "purify" the blood, and another group without or with minimal urine production, who, in addition to blood purification, are in need of a significant fluid removal.

Number of Patients

The study population consists of 15 patients with minimal fluid removal during dialysis and 15 patients in need of fluid removal exceeding 2000 ml.

According to earlier experience, 15 patients in each group should be sufficient to clearly observe a pattern in fluid recruitment from the tissues (lymph or pericapillary fluid). For 80% power at 25% difference in fluid recruitment balance between the groups and a standard deviation of 20%, at least 11 patients should be recruited to each group to achieve a significance level below 0.05 with a T-test or Wilcoxon (if the material is not normally distributed).

Recruitment and Consent

Patients receiving hemodialysis regularly at the dialysis department at Vrinnevi Hospital in Norrköping are screened if they are expected to meet the inclusion criteria for the study.

Those who meet the inclusion criteria and have no exclusion criteria to participate are asked for participation and consent. Consent is obtained by one of the investigators verbally and in writing, during a hemodialysis session prior to the actual study procedure.

Inclusion Criteria:

Patients receiving hemodialysis (<500 ml or >2000 ml ultrafiltration):

Signed informed consent that the patient accepts participation in the study after oral and written information.

Exclusion Criteria:

Patients who may be affected by blood sampling, i.e., have low hemoglobin concentration, independent of dilution before dialysis (Hemoglobin 85 g/L).

Patients who drink large amounts of water during regular dialysis (> 2 glasses, approximately 0.4 L).

The study is discontinued in case of a severe reaction (even if not related to the study), such as the need to interrupt dialysis. The patient or participant may also choose to discontinue participation in the study at any time.

Intervention and Procedures

Patients in need of dialysis and who regularly undergo dialysis at the dialysis unit at Vrinnevi Hospital in Norrköping are asked to participate in the study. Patients who are eligible are those who have fluid removal of either <500 ml or >2000 ml. These patients are approached during a routine dialysis visit to the dialysis unit. If the response is positive, a trial session is planned for a later date.

Before dialysis begins, the patient is weighed. Then, the regular dialysis procedure starts, with the dialysis machine being connected. At the same time, Bioimpedance is also connected to the patient, and values for lean body mass (LBM), fat mass (FM), ECV, and ICV are recorded. Pulse and blood pressure are also recorded. Once the dialysis machine is connected with an intravenous access, the first blood samples, i.e., "zero samples," are taken. Dialysis then commences.

The selected dialysate is recorded, as well as the continuous fluid removal and blood pressure. Blood samples are taken every 30 minutes for 150 minutes (Hb, hematocrit, albumin, Immunoglobulins G and M, and colloid osmotic pressure (COP)), bioimpedance values are recorded, and pulse and blood pressure are registered. This continues until the end of dialysis. At the end of dialysis, the final samples and measurements are taken. The patient is weighed once again.

Fluid intake if it occurs is also recorded. When the patient leaves the dialysis unit, the study concludes.

In case of pressure drops, these are treated in the usual manner, i.e., the patient is placed in the Trendelenburg position or supplemented with Albumin 20%. Measures are recorded.

In total, blood sampling amounts to approximately 50 ml, at most 75 ml, equivalent to 3 to 5 tablespoons.

Measurements

Weight is taken before and after dialysis.

Bioimpedance is connected and values for body composition, i.e., lean body mass (LBM), fat mass (FM), ECV, and ICV are recorded before and after dialysis, as well as during blood sampling.

Hb, albumin, Ig G + M, and COP are measured and analysed before, at 1, 30, 60, 90, 120, and possibly at 150 minutes after the initiation of hemodialysis, as well as at the end of dialysis. These samples are taken from the access (cannula) used during dialysis. Therefore, no additional punctures are needed.

Fluid removal and any spontaneous diuresis are recorded. Patients with spontaneous diuresis are asked to urinate before and after dialysis.

Oral fluids consumed during dialysis are recorded.

Risk- Benefit assessment

Disadvantage for patients is a loss of approximately 50 to 75 ml of blood, which corresponds to half a decilitre of blood (3 to 5 tablespoons) (about 1% of the total blood volume). In connection with the study, there is enhanced monitoring, and the closer pressure and pulse controls can detect an impending drop in blood pressure slightly earlier.

The advantage of the study is more long-term. The study contributes to mapping how the recruitment of fluid/oedema from the interstitium occurs. Consequently, one should be able to more easily predict potential drops in blood pressure by taking preventive measures such as adjusting composition of dialysate and rate at which the hemodialysis is performed.

Treatment and administration of other medications

Hemodialysis is performed according to standard procedures. No restrictions on the administration of medications or treatments will be made, except for a selection of patients who do not drink more than 2 glasses, approximately 0.4 litres of water, during regular dialysis sessions.

The study does not affect the patient's ongoing care or management.

Studied data/Registration of effects

Changes in Hemoglobin, albumin, and COP during hemodialysis

Changes in plasma volume are calculated partly using changes in Hemoglobin and partly using Mass Balance calculations.

Once all samples are analyzed, any remaining blood/plasma is destroyed.

Mass balance

Plasma volume. Initial blood volume calculated with the Nadler formula ⁷.

BV_0 , based on height h , (meters), weight w (kg) and gender.

Men: $BV_0 = 0.3669 h^3 + 0.03219 w + 0.6041$

Female: $BV_0 = 0.3561 h^3 + 0.03308 w + 0.1833$

How mass balance calculations will be performed is described in a work on 5% albumin solution. ^{5,6}. Total mass hemoglobin at study start is calculated from BV_0 and hemoglobin at start of hemodialysis, Hb_0 ; ⁷

$$MHb_0 = BV_0 \times Hb_0$$

Blood volume (BV) at a later occasion, t , is calculated in a similar manor;

$$BV_t = \frac{MHb_t}{Hb_t}$$

Plasma volume (PV) is calculated;

$$BV_t (1 - Hct_t) = PV_t$$

The percentage increase/decrease in plasma volume will then be ($\Delta PV\%$);

$$\frac{PV_t - PV_0}{PV_0} \times 100 = \Delta PV\%$$

Recruited fluid (RE) from the tissue is based on the change in plasma volume and total diuresis/fluid removal. However, this volume must be corrected for diuresis and ingested fluid.

$$RE_{extravascular} = Ultrafiltrate + Diuresis - Ingested + (PV_t - PV_0)$$

Statistics and Data Processing

The study aims to follow a fluid kinetic process. In previous studies, we routinely used 10 healthy subjects to study similar processes. This has been sufficient to describe clear trends and differences in how the body responds to fluid infusions. However, in this study, we increase the number of participants to fifteen in each group to even more clearly establish the processes.

As there are only two groups to be compared, a t-test will primarily be used for the primary variable, i.e., the effect on plasma volume. For secondary variables, chi-square tests will be used. In the case of non-normally distributed data, Wilcoxon's test will be used instead.

Safety Regulation

The study will be conducted according to the protocol and applicable regulations, LVFS 2011:19, ICH GCP, and the latest version of the Helsinki Declaration. Patients will be monitored in the usual manner in the dialysis department.

Quality Assurance

- relevant health status data from medical records or health declaration
- signed consent
- The study is conducted in accordance with the protocol

Study Director [name] participated in a GCP course at Linköping University Hospital on April 25 - 26, 2007, and subsequently conducted several studies approved by the Medical Products Agency.

Ethics

Patients are approached for participation in a calm stage when they are receptive to information. If there is potential interest from the patient to participate, the study investigator informs the patient about the study. The responsible physician obtains the patient's written consent, and a copy of the signed consent form is provided to the patient.

The care for the individual patient is minimally affected. Patients will not be impacted in any other way except for undergoing additional tests. However, it may be necessary to retrieve information from the medical record, which could potentially be seen as an intrusion into personal privacy.

Participation in the study is noted in the medical record.

The longer-term benefit of the study would be that through a better understanding of fluid dynamics, hemodialysis for dialysis-dependent patients could be tailored in a physiologically better way.

Source Data/Original Data and Archiving

Laboratory analyses (e.g., B-Hb, P-albumin...) conducted by the laboratory medicine department will be requested in printed form, so that they can be sorted into binders and used as reliable primary data when needed. Analyses conducted by the study group themselves (e.g., colloid osmotic pressure) will be immediately entered into the patient's Case Report Form (CRF) at the time of analysis. All study-related data (CRF and laboratory results) will be recorded in "CRF binders," with all collected information divided by individual patients. All CRF binders will be kept locked and only accessible to the trial team.

As the data are entered into Excel spreadsheets (i.e., computerized), they will be de-identified. However, a source data verification list will be established. This list will only be accessible to the investigators. The Patient ID list, which is only accessible to the trial team, and other study-related documents will be archived and stored for at least 15 years after the end of the study.

Insurance

Region Östergötlands insurances apply.

Publications/Timeframe

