1.1. Population to be analyzed

- In the protocol 15 patients are included in each group, with the ambition to reach totally 30 evaluable patients (per protocol), defined as patients completing the study. If a patient is excluded during or before the study, the patient will be replaced. Patients excluded from the study after inclusion will be accounted for as dropouts.
- The study will be performed in Norrköping.

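### The printed recruitment equation has no term for an Albumin 20% rescue infusion, and no printed rule keeps its albumin out of the lymph share

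*Protocol*

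**What the plan says.** **Outcome.** The protocol (Outcome Measures) lists two primary outcomes. One is fluid recruited from the interstitium. The other is "Proportion of recruited fluid via lymph or via capillary/venular walls based on fluid recruitment and changes in plasma albumin and immunoglobulins G and M". The SAP (1.2.1 and 1.3) makes recruitment the primary variable and puts the lymph share in the secondary analysis.

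**Principle of the split.** The Synopsis takes fluid drawn across the capillary wall to bring in little protein, and then says: "This differs from lymph, where albumin and immunoglobulins are present".

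**Rescue.** For a pressure drop, under Intervention and Procedures, "the patient is placed in the Trendelenburg position or supplemented with Albumin 20%. Measures are recorded". Time, volume and strength are not itemised.

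**Equation.** Under Mass balance, with UF for ultrafiltrate, D for diuresis and I for ingested fluid, RE = UF + D - I + (PV_t - PV_0). The text names these corrections only: "However, this volume must be corrected for diuresis and ingested fluid". Under Measurements, the intake recorded is oral.

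**Method reference.** "How mass balance calculations will be performed is described in a work on 5% albumin solution". No equation for the lymph share is printed.

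**Who is analysed.** SAP 1.1 aims for "totally 30 evaluable patients (per protocol), defined as patients completing the study". Drop-outs (SAP 1.2.2) are non-completers, so a rescued patient who finishes stays in. The SAP has no exclusion, censoring, subtraction or sensitivity rule for patients given albumin.

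**The concern.** Intravenous albumin enters the calculation in two places. Its volume raises PV_t, and the printed equation then attributes that rise to fluid from the tissues. Its protein raises plasma albumin, which is one of the three signals that the plan reads as lymph.

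The error is unlikely to be balanced between groups. The Background gives ultrafiltration as the main cause of hypotension, and the Synopsis links it to removal above 400 ml/hour. Removing more than 2000 ml exceeds that rate in any session of up to 2000/400 = 5 hours. Rescue should therefore fall mostly in the >2000 ml group. An upward error there would hide a truly lower lymph share and exaggerate a truly higher one. The documents predict no direction.

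**Working it through.** **1. The plan's own figure.** SAP 1.4: difference 25, SD 20, two-sided 0.05, power 80%. Normal approximation: n = 2 x (1.960 + 0.842)^2 x 20^2/25^2 = 10.05, so 11 per group, as stated. An exact t-test has 79.6% power at 11 and 91.0% at the planned 15. The point does not depend on this figure, but 91% is the reference below.

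**2. Volume, from the printed equation.** Plasma balance with an infused volume V gives PV_t - PV_0 = RE - UF - D + I + V. Hence true RE = UF + D - I - V + (PV_t - PV_0). The printed equation omits V and is too high by exactly V. With V = 100 ml and 2 L recruited, the error is 100/2000 = 5% in that patient. One or two such patients among 15 shift the group mean by 100/15 = 7 ml or 200/15 = 13 ml.

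**3. Lymph share, if infused albumin is not removed.** None of these inputs is in the documents; all are assumed:
- 100 ml of Albumin 20% (20 g), none leaking out of plasma
- plasma albumin 35 g/L, lymph albumin 50% of that (range 30-70%)
- 2.0 L recruited, true lymph share 30% (0.60 L)
- the three markers averaged equally

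Lymph albumin is 35 x 0.5 = 17.5 g/L, so 20 g looks like 20/17.5 = 1.14 L of lymph.
- Albumin share: (0.60 + 1.14)/2.1 = 0.830, error +53 points.
- IgG/IgM share: 0.60/2.1 = 0.286, error -1.4 points, caused by the volume alone. With the infusion term it returns to 0.60/2.0 = 0.30.
- Three-marker mean: (0.830 + 2 x 0.286)/3 = 0.467, error +16.7 points.

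| Lymph albumin, % of plasma | Albumin share | Error in three-marker mean |
|---|---|---|
| 70% | 0.674 | +11.5 |
| 50% | 0.830 | +16.7 |
| 30% | 1.193, capped at 1.00 | +22.4 |

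With 10 g in 50 ml, or with 4 L recruited, the error is +8.6 points.

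**4. Effect on the comparison.** At +16.7 points, one or two rescues among 15 shift the group mean share by 16.7/15 = 1.1 or 33.4/15 = 2.2 points. Simulated t-test, 15 v 15, SD 20 assumed for the share, error added to 0, 1 or 2 patients in the >2000 ml group:

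| Error | True difference | 0 rescues | 1 | 2 |
|---|---|---|---|---|
| +16.7 | -25 | 91% | 88% | 84% |
| +22.4 | -25 | 91% | 87% | 81% |
| +16.7 | 0 | 5.0% | 5.0% | 5.4% |
| +16.7 | +25 | 91% | 93% | 95% |

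**5. How often.** The Background puts hypotension at "occurring in about 10% of treatment sessions according to previous studies". If half of those sessions got albumin (assumed), the rate is 5%, or 0.75 expected among 15. The chance of none is 0.95^15 = 46%, of at least one 54%, of two or more 17%. Averaged over this distribution, power at a true difference of -25 is 88.6%, against 91.1% with no rescue.

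**The case against.** The strongest objection is that the plan delegates the mass balance to a work on an albumin infusion, and Outcome Measures attaches the same references to recruitment. The Background adds that the route of recruitment has been measured during albumin infusion, "depending on the concentration of proteins such as IgG and IgM over time". A method from that setting is a natural place for infused volume and protein to be handled. This stands for the lymph share. A reader might infer that the plan counts infused albumin as lymph, but the documents do not show that: the share equation is not printed and the cited work is not available here. It does not remove the volume point, because the equation printed for this study has no infusion term.

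Second, rescue measures are already recorded, so correction is possible at analysis if volume and strength are in the record. That is fair, but a record is not a rule. Without one, the choice is made after open-label data have been seen.

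Third, the size is mostly assumed, and equal averaging of the markers drives the 17 points. This stands too, so the figures are illustrations. A reader might take the 30% row uncapped, which gives an error of 29 points and power of 76% with two rescues. That requires accepting an albumin share of 119% without question, so the capped values are the ones to use.

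Fourth, some severe episodes never reach the analysis, because patients whose dialysis must be interrupted are discontinued and replaced. Samples taken before an infusion are also unaffected. Both limit the reach.

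**Conclusion.** The volume error follows from the printed equation: recruitment is overstated by the infused volume in any completing patient given Albumin 20%. It is about 5% per 100 ml at 2 L recruited and negligible for the group mean. A reader might infer that the SAP's primary variable is at risk; a shift of 7 to 13 ml in the mean does not support that.

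The lymph-share error is conditional on the cited method not removing infused albumin. If it does not, an affected patient's three-marker share is about 17 points too high (12 to 22) under the assumed inputs, and that patient's result is not interpretable. The group comparison changes little: 1 to 2 points in the mean, a few points of power in either direction (down to 81% with two rescues at the 22-point error), and type I error near 5%. There may be no rescued patient at all. This is a low-priority clarification that could be made, worth doing because it costs almost nothing.

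**What to change.** 1. **CRF:** within the measures already recorded, enter the time, volume and strength of any albumin given.
2. **Protocol, Mass balance:** RE = Ultrafiltrate + Diuresis - Ingested - Infused + (PV_t - PV_0).
3. **SAP 1.2.1, proposed wording:** *If any patient receives albumin, the main between-group comparison of the lymph share uses IgG and IgM only, in all patients of both groups. One sensitivity analysis excludes patients given albumin.*

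This names one main result and applies one estimator to both groups. If the cited method already subtracts infused volume and albumin mass, one sentence saying so replaces items 2 and 3.

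**Cost:** one CRF line, one term and two sentences. There is no extra sampling, because IgG and IgM are already measured, and no change in how pressure drops are treated. The downside is two markers instead of three: marker-error SD rises by sqrt(3/2) = 1.22, about 22%, if errors are equal and independent. Subtracting the albumin mass would keep three markers but assumes no leakage. If 20% of a 20 g dose had left plasma, the share would be 0.2 x 20/17.5/2.0/3 = 3.8 points too low. Neither option removes fluid that the albumin itself draws in, which is real recruitment.

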1.2. Statistical analysis

1.2.1. Statistical method

- A two-sided test of significance will be used.
- After the last patient has been included an evaluation will be made if results are distributed according to the norm. If so, parametrical statistical methods will be used i.e., T-test.
- If these are not distributed according to the norm the Wilcoxon test will be used.
- Recruitment of fluid is the primary variable.

If the study is dissected, it contains two groups:

- A. Patients with a fluid withdrawal of less than 500 ml
- B. Patients with a fluid withdrawal of more than 2000 ml

Statistical processing of the primary outcome

In the first analysis total recruitment of fluid from the tissues will be evaluated.

Total recruitment and AUC (Area under the curve) for recruited fluid, i.e., fluid removal and hemoglobin changes. Moreover, the inverted half-life for recruitment will be determined.

In the secondary analysis, the proportions of the fluid recruitments via lymph or via capillary/venular walls will be performed

Methods: One way test, T-test or Wilcoxon.

Secondary outcome

Weight, blood pressure and changes in bio-impedance variables will be correlated to withdrawal of fluid.

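### Correlating within-session weight change with fluid withdrawal is largely circular, and fat and lean mass add little; the weights are better used to check the recorded fluid balance

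*Protocol*

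**What the plan says.** The protocol (Outcome Measures) lists the secondary outcomes as "Weight, blood pressure and changes in bioimpedance variables". SAP 1.2.1 gives their analysis: "Weight, blood pressure and changes in bio-impedance variables will be correlated to withdrawal of fluid". It does not name a coefficient or a time point, and it does not say whether the two groups are pooled. The protocol's Statistics and Data Processing section gives a different method: "For secondary variables, chi-square tests will be used".

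On measurement, the protocol states: "Weight is taken before and after dialysis". For bioimpedance, "values for body composition, i.e., lean body mass (LBM), fat mass (FM), ECV, and ICV are recorded before and after dialysis", and also at each blood sampling. Follow-up is a single session: "When the patient leaves the dialysis unit, the study concludes".

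The Mass balance section calculates recruited fluid as RE = U + D − I + (PV_t − PV_0), where U is ultrafiltrate, D diuresis and I ingested fluid. The groups are defined by U below 500 ml or above 2000 ml, with nobody between. SAP 1.3 plans no multiplicity correction for secondary outcomes, but promises to consider the problem when interpreting them.

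**The concern.** Over one session a patient's weight falls by about what is removed and passed, less what is drunk. These are the external terms of RE, and U is itself the withdrawal. A correlation between weight change and withdrawal therefore mostly confirms bookkeeping and says little about recruitment. Fat mass and possibly lean mass raise a related problem: a correlation may show only how the device assigns lost water.

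Two things are at stake. Coefficients that are nearly certain in advance, or artefacts, could be reported as secondary findings. A useful check is also missed. An error in recorded ultrafiltrate, diuresis or intake enters RE, the primary outcome, one for one. The two weighings bear directly on that balance, but a correlation coefficient ignores a constant offset and so cannot show such a bias.

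**Working it through.** **The plan's own figure.** SAP 1.4 gives 11 per group for a difference of 25%, SD 20%, two-sided 5% and 80% power. n = 2 × (1.960 + 0.842)² × (20/25)² = 10.05, rounded up to 11. This reproduces and does not bear on the point.

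**Inputs from the documents.** There are 15 patients per group, with U below 500 ml or above 2000 ml. Intake is limited to about 400 ml by the exclusion criterion. Sampling loss is 50 to 75 ml.

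**Assumptions (not in the documents), ml.** All are uniform except scale error: U 0–500 or 2000–4000; diuresis 0–300 in the low group or 0–50 in the high group; intake 0–400; insensible loss 0–200. The scale error of the weight difference has SD s = 50 to 300. The variance of a uniform variable is (range)²/12.

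**Within each group.** r = √[Var(U) / (Var(U) + V + s²)], where V is the variance of the other terms.

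- <500 ml: Var(U) = 500²/12 = 20,833. V = 7,500 + 13,333 + 52 + 3,333 = 24,219 (summed before rounding). With s = 50, r = √(20,833/47,552) = 0.66. With s = 300, r = √(20,833/135,052) = 0.39.
- >2000 ml: Var(U) = 2000²/12 = 333,333. V = 208 + 13,333 + 52 + 3,333 = 16,927 (summed before rounding). With s = 50, r = √(333,333/352,760) = 0.97. With s = 300, r = √(333,333/440,260) = 0.87.

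**Pooled.** The group means of U are 250 and 3000, a gap of 2750. The expected weight losses differ by 2750 − 125 = 2625, because mean diuresis is 150 against 25.

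- Var(U) = (20,833 + 333,333)/2 + 2750²/4 = 2,067,708.
- Covariance = 177,083 + 2750 × 2625/4 = 1,981,771.
- Var(weight loss), s = 50: (47,552 + 352,760)/2 + 2625²/4 = 1,922,812, so r = 1,981,771/√(2,067,708 × 1,922,812) = 0.994.
- Var(weight loss), s = 300: 2,010,312, so r = 0.972.

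In 2,000 simulated studies per setting the median r agreed:

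| Weight variable | Pooled | <500 ml | >2000 ml |
|---|---|---|---|
| Change, s = 50 | 0.994 | 0.68 | 0.98 |
| Change, s = 300 | 0.975 | 0.40 | 0.88 |
| Absolute post-dialysis weight, SD 15 kg | −0.09 | −0.01 | −0.05 |

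The pooled correlation for weight change was significant in every run. The model contains no recruitment physiology.

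**Fat mass.** Suppose the true change is nil and the device assigns a fraction k of withdrawal to fat, with error SD e. Then r = k·SD(U)/√(k²Var(U) + e²), with SD(U) = √2,067,708 = 1438.

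- k = 0: r about 0, significant in about 5% of runs.
- k = 0.10, e = 1000: 143.8/√(20,677 + 1,000,000) = 0.14 (simulated 0.15, significant in 12%).
- k = 0.25, e = 300: 359.5/√(129,232 + 90,000) = 0.77 (simulated 0.78, significant in 100%).

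**ECV.** If 60–100% of withdrawal comes from ECV and e is 300 to 500, pooled r is 0.91 to 0.95, but 0.23 to 0.37 in the low group and 0.62 to 0.72 in the high group. The gap between groups drives the pooled figure here too, so ECV should be reported by group.

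**How well the weights could check the balance.** Let d = weight loss − (ultrafiltrate + diuresis + sampling loss − ingested − infused). With 0.1 kg SD per weighing and insensible-loss SD 0.05 kg, SD(d) = √(0.01 + 0.01 + 0.0025) = 0.15 kg. A 0.3 kg trigger around the mean then flags a true 0.3 L error about half the time and a 0.5 L error 91% of the time (0.2/0.15 = 1.33 SD). With no errors it flags 4.6% of patients, about 1.4 of 30. With s = 300 ml, SD(d) = √(90,000 + 3,333) = 306 ml and false flags rise to about 33%.

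**The case against.** Several stronger readings are tempting, and the documents do not support them.

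- **Weight change is the withdrawn fluid itself, in every group.** This fails in the <500 ml group, where withdrawal accounts for under half of the variance in weight change (0.66² = 0.44 at best). SAP 1.2.1 also says weight, not weight change, and absolute weight would not be built in.
- **Fat and lean mass are listed outcomes that cannot change.** They appear in the measurement list, not in Outcome Measures, and the SAP does not single them out. The documents do not say whether lean body mass includes water. If it does, it truly falls with withdrawal. That fat mass is stable over a session is physiological reasoning, not a statement in the plan.
- **The weights are the only check on recorded ultrafiltrate.** ECV and ICV give another, noisier view. A plot of weight change against withdrawal would also show gross discordance.
- **A 0.3 kg rule would expose recording errors.** It would miss about half of those of 0.3 L, and it rests on assumed errors.

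It is also fair to say that these outcomes are secondary and unpowered, that SAP 1.3 promises caution, and that nothing in the documents suggests unreliable recording. These points limit the size of the concern. They do not give the pooled weight-change correlation any information about recruitment.

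**Conclusion.** The concern holds in limited form. If weight means within-session change, its pooled correlation with withdrawal is about 0.975 to 0.994 by construction. The figure is 0.88 to 0.98 in the >2000 ml group and 0.40 to 0.68 in the <500 ml group. These ranges rest on assumed withdrawal, diuresis, insensible loss and scale error. A fat-mass correlation would be noise or misassigned water. A lean-mass correlation would be largely built in or an artefact, depending on a definition that the plan does not give. Blood pressure, ECV and ICV remain legitimate outcomes.

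A reader might infer that the primary result is compromised. It is not: the planned primary test and the sample size are unaffected. What is lost is a check on the inputs to RE that the collected data already allow. The protocol and SAP also disagree on the secondary method, and a chi-square test does not suit these continuous variables.

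**What to change.** In the SAP:

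1. Define weight as within-session change. Replace its correlation by d, as defined in the working, for each patient, with mean and limits of agreement by group. The mean should be near the insensible loss, not zero. State whether voids before and after dialysis fall inside or outside the two weighings, since this decides whether they enter d.
2. Check outlying values of d against source documents, without a fixed 0.3 kg cut-off.
3. Repeat RE with weight-based loss as a sensitivity analysis, noting that this adds scale error and insensible loss.
4. Name changes in ECV and ICV as the bioimpedance outcomes, reported by group. Use pre-dialysis lean and fat mass as descriptors only.
5. Reconcile the SAP's correlation with the protocol's chi-square test, and name a method for continuous data.

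The cost is wording, slightly more analysis and fewer secondary correlations. No new measurements are needed.
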